#### 9. DATA COLLECTION

An electronic data capture (EDC) system will be used for this trial. All users will be trained on the technical features of the EDC as well as the content of the eCRF by qualified personnel prior to gaining access to the EDC. A User ID/Password will be granted after training. This ID is not to be shared amongst the study staff. All users must have a unique account to enter or review data. The eCRF should be filled out by the site 5 days after the Day 7 visit and 3 days after the Day 14 visit. It is not expected that the eCRF will serve as source for any data collected in this trial. If there is a reason for a site to do so, it must be approved by MDCO and documented in the site files.

Prior to the database being locked, the investigator or designee will review, approve and sign/date each completed eCRF. This signature serves as attestation of the Investigator's responsibility for ensuring that all data entered into the eCRF are complete, accurate and authentic. After the end of the trial, a copy of the data will be provided to the site. This copy will contain the final data, an audit trail of activity on the data, and any queries and answers that were posted for data clarification.

#### 10. STATISTICAL PLAN

The primary objective of this study is to assess the safety and tolerability when a single 1200 mg infusion of oritavancin is given concomitantly in subjects on chronic warfarin with ABSSSI. Statistical methods and data presentation will be described in more detail in the Statistical Analysis Plan (SAP) document.

#### 10.1. SAMPLE SIZE

The sample size of 25 subjects on concomitant warfarin therapy is chosen based on feasibility and clinical judgment to provide adequate safety information on the administration of oritavancin with an ABSSSI who are on chronic warfarin.

An additional group of 15 ABSSSI patients, who are not on chronic warfarin therapy, was added to obtain information regarding potential for antibody production related to oritavancin administration.

#### 10.2. GENERAL STATISTICAL CONSIDERATIONS AND DEFINITIONS

#### 10.2.1. General Statistical Methods

Continuous variables will be summarized using mean, standard deviation (SD), median, quartiles (Q1 and Q3), minimum, and maximum. Categorical variables will be summarized using frequency and percentage.

# 10.2.2. Analysis Population

Two populations will be used for data analyses and/or presentation.

#### 10.2.2.1. Intent-to Treat (ITT) Population

The ITT population will include all subjects screened and enrolled. This will be the primary population for efficacy analysis.

# 10.2.2.2. Safety Population

The safety population will include all subjects who are dosed with IV oritavancin. This will be the primary population for safety analysis.

# 10.2.3. Analysis Windows and Baseline

Unless otherwise specified, the last evaluation prior to the initiation of dosing will be considered the "Baseline" evaluation for analysis of data.

# 10.2.4. Missing Data Handling

Unless otherwise specified, missing data will not be imputed and will be excluded from the associated analysis.

## 10.3. STATISTICAL ANALYSES

All summaries will be presented by group.

# 10.3.1. Demographic and Background Characteristics

Subject demographics and baseline characteristics will be summarized using the safety population.

#### 10.3.2. Prior and Concomitant Medications

Separate summaries of prior and concomitant medications will be provided for the safety population. Prior medications are those received before the initiation of dosing on Day 1 while concomitant medications are those received after. Medications will be coded with the World Health Organization (WHO) Drug Dictionary Enhanced.

## 10.3.3. Safety Analysis

### 10.3.3.1. Adverse Events

The Medical Dictionary for Regulatory Activities (MedDRA) will be used for coding AEs. An AE (classified by system organ class and preferred term) that occurs during the treatment period will be counted as a treatment-emergent AE (TEAE) either if it is not present at Baseline or if it is present at Baseline but increased in severity during the treatment period or follow up period.

The number (percentage) of subjects reporting TEAEs for each preferred term will be tabulated by system organ class, by system organ class and severity, and by system organ class and relationship to oritavancin. If more than 1 event occurred with the same preferred term for the same subject, the subject will be counted only once for that preferred term using the most severe or related occurrence for the summary by severity, or relationship to study drug, respectively.

Listings of SAEs and AEs leading to treatment or study discontinuation will also be provided.

# 10.3.3.2. Clinical Safety Laboratory Tests

Clinical safety laboratory values and changes from Baseline, including prothrombin time (PT)/international normalized ratio (INR), direct and indirect Coombs, Immunoglobulin panel, oritavancin antibody assay, will be summarized descriptively. Clinically significant (CS) values will also be flagged in a listing.

### 10.3.3.3. Vital Signs

Vital sign measurements and changes from Baseline will be summarized descriptively at each scheduled time point. Potentially clinically significant changes will also be flagged in a listing.

#### 11. RECORDS RETENTION

Current Food and Drug Administration (FDA) regulations require all investigators participating in clinical drug trials to maintain detailed clinical data for one of the following periods:

- At least 2 years following the date on which a New Drug Application is approved by the FDA, or
- Two years after the Sponsor notifies the investigator that no further application is to be filed with the FDA

Similarly, International Conference on Harmonization (ICH) guidelines require that essential documents be retained until at least 2 years after the last approval of a marketing application in an ICH region and until there are no pending or contemplated marketing applications in an ICH region or at least 2 years have elapsed since the formal discontinuation of clinical development of the investigational product.

To comply with these requirements, the investigator will not dispose of any records relevant to this study without either (1) written permission from the Sponsor or (2) providing an opportunity for the Sponsor to collect such records. The investigator shall take responsibility for maintaining adequate and accurate hard copy source documents of all observations and data generated during this study, including any data clarification forms received from the Sponsor. Such documentation is subject to inspection by the Sponsor or its agents, the FDA and/or other regulatory agencies.

# 12. QUALITY CONTROL AND QUALITY ASSURANCE

#### 12.1. MONITORING

The Sponsor has ethical, legal, and scientific obligations to carefully follow this study in accordance with established research principles and applicable regulations. The investigator, as part of his responsibilities, is expected to cooperate with the Sponsor in ensuring that the study adheres to the protocol and GCP requirements.

As part of a concerted effort to fulfill these obligations, the Sponsor's monitor will visit the study center during the study in accordance with the Monitoring Plan set forth for this trial. The investigator will permit the Sponsor to monitor the study as frequently as is deemed necessary and provide access to medical records/source documents to ensure that data are being recorded adequately, that data are verifiable, and that protocol adherence is satisfactory.

#### 12.2. AUDITING

The Sponsor may conduct audits at the study centers. Audits will include, but will not be limited to, drug supply, presence of required documents, the informed consent process, and comparison of eCRFs with source documents. The investigator agrees to permit audits conducted at a reasonable time in a reasonable manner.

Regulatory authorities worldwide may also inspect the investigator during or after the study. The investigator should contact the Sponsor immediately if this occurs, and must permit regulatory authority inspections.

#### 12.3. PROTOCOL DEVIATIONS

This study will be conducted as described in this protocol, except for an emergency situation in which the protection, safety, and well-being of the subject requires immediate intervention, based on the judgment of the investigator (or a responsible, appropriately trained professional designated by the investigator).

In the event of a significant deviation from the protocol due to an emergency, accident, or mistake, the investigator or designee must contact the Sponsor (Clinical Project Director, Medical Director or Clinical Research Associate) at the earliest possible time. This will allow an early joint decision regarding the subject's continuation in the study. The investigator and the Sponsor will document this decision.

The IRB/EC will be informed of all protocol changes by the investigator in accordance with the IRB/EC-established procedure. No deviations from the protocol of any type will be made without complying with all IRB/EC-established procedures.

Any protocol deviations that will affect the subject's safety or the study objectives may be considered a Major Protocol Deviation upon review by the Sponsor. In addition, any of the following deviations will be considered Major Protocol Deviations:

# Inclusion/Exclusion Criteria deviations:

- Subject is < 18 years of age.
- Subject has a condition, including findings in the medical history or in pre-study assessments that constitutes a risk or a contraindication for the participation in the study or completing the study.
- Subject has a history of hypersensitivity to drugs with a similar chemical structure (i.e. glycopeptide antibiotics) to the investigational product or any of its excipients.

# Dosing deviation:

• Subject is given an incorrect dose of oritavancin.

#### 13. ETHICS AND RESPONSIBILITY

This study will be conducted in compliance with the protocol, the Sponsor's standard operating procedures and/or guidelines, the United States regulations, the ICH GCP guidelines, the Declaration of Helsinki, and other local regulations, as applicable.

#### 13.1. INFORMED CONSENT

Written informed consent will be obtained from all subjects or, as per IRB/EC guidelines, before any study-related procedures (including any pretreatment procedures) are performed. The investigator has both ethical and legal responsibilities to ensure that each subject being considered for inclusion in this study is given a full explanation of the protocol. This shall be documented on a written informed consent form, which shall be approved by the same IRB/EC responsible for approval of this protocol. Each informed consent form shall include the elements required by ICH, Part E6, Section 4.8 and any applicable local regulations. The investigator agrees to obtain approval from the Sponsor of any written informed consent form used in the study, preferably prior to submission to the IRB/EC.

Once the appropriate essential information has been provided to the subject and fully explained by the investigators (or a qualified designee) and the subject indicates an understanding of the implications of participation, the subject and the investigator (or designee) shall sign the IRB/EC-approved written informed consent form. The subject shall be given a copy of the signed informed consent form and the original shall be filed appropriately, according to the institution. A second copy may be filed in the subject's medical record, if allowed by the institution.

#### 13.2. ETHICS COMMITTEE/INSTITUTIONAL REVIEW BOARD

This protocol, the written informed consent form, and any materials presented to subjects shall be submitted to the IRB/EC identified with this responsibility. Notification in writing of approval must come from the IRB/EC chairman or secretary, to the investigator, either as a letter or as a copy of the appropriate section of the IRB/EC meeting minutes where this protocol and associated informed consent form were discussed. The investigator will not participate in the decision. If the investigator is an IRB/EC member, the written approval must indicate such nonparticipation in the voting session. The investigator will submit status reports to the IRB/EC as required by the governing body. The IRB/EC must be notified by the investigator in writing of the interruption and/or completion of the study; the investigator must promptly report to the IRB/EC all changes in research (protocol amendments) and will not make such changes without IRB/EC approval, except where necessary to eliminate apparent immediate hazards to subjects, the IRB/EC must then be notified of the change as per local requirements. The investigator is required to maintain an accurate and complete record

of all written correspondence to and received from the IRB/EC and must agree to share all such documents and reports with the Sponsor.

# 14. CONFIDENTIALITY

All information generated in this study must be considered highly confidential and must not be disclosed to any persons not directly concerned with the study without written prior permission from the Sponsor. However, authorized regulatory officials and Sponsor personnel will be allowed full access to the records. All medications provided and subject bodily fluids and/or other materials collected shall be used solely in accordance with this protocol, unless otherwise agreed to in writing by the Sponsor.

Only unique subject numbers in eCRFs will identify subjects. Their full names may, however, be made known to a product regulatory agency or other authorized official if necessary.

HEENT	head, eyes, ears, nose, throat
HIV	Human Immunodeficiency Virus
IAT	Indirect Coombs Test (DAT)
ICH	International Conference on Harmonisation
IgA	Immunoglobulin A
IgE	Immunoglobulin E
IgG	Immunoglobulin G
IgM	Immunoglobulin M
INR	International Normalized Ratio
IRB	institutional review board
ITT	Intent-to-Treat
IV	intravenous
LLN	lower limit of the standard reference (normal) range
MDCO	The Medicines Company
MedDRA	Medical Dictionary for Regulatory Activities
MI	myocardial infarction
MIC	Minimum Inhibitory Concentration
MRSA	methicillin-resistant S. aureus
No.	Number

Abbreviation	Explanation
OTC	over the counterPotentially clinically significant (PCS)
PCS	Potentially clinically significant
PK	pharmacokinetic
PT	prothrombin time
Q1	first quartile
Q3	third quartile
SAE	serious adverse event
SAP	statistical analysis plan
SD	standard deviation
SOC	standard of care
TEAE	treatment-emergent adverse event
T _{1/2}	Half-life
T _{1/2,α}	Half-life for the alpha phase
T _{1/2,β}	Half-life for the beta phase
T _{1/2,γ}	Half-life for the gamma phase
ULN	Upper limit of the standard reference (normal) range
US	United States
USP	United States Pharmacopeia
USPI	United States Package Insert
V _{ss}	steady-state volume of distribution
WHO	World Health Organization

1 INTRODUCTION

This statistical analysis plan (SAP) describes the statistical analysis methods and data presentation to be used for the analysis and summarization of safety data from Protocol MDCO-ORI-14-03, Amendment 2 (17 March 2016).

The analysis plan will be finalized prior to database lock, but may change due to unforeseen circumstances. Any changes made after finalization of the analysis plan will be documented. Related documents are the study protocol and electronic case report forms (eCRFs).

2 OBJECTIVES AND ENDPOINTS

2.1 Primary Objectives

- To assess the safety and tolerability when a single 1200 mg intravenous (IV) infusion of oritavancin is given concomitantly in subjects on chronic warfarin therapy with acute bacterial skin and skin structure infection (ABSSSI).
- An additional group of patients with ABSSSI, who are not on concomitant warfarin therapy, will be enrolled to obtain information regarding the potential for antibody production following a single dose of oritavancin administration in patients.

2.2 Secondary Objective

Not applicable.

2.3 Endpoint

2.3.1 Primary Endpoint

The primary endpoint of this trial is:

- Safety of the administration of oritavancin in subjects on chronic warfarin will be assessed according to vital signs, laboratory abnormalities, and the incidence of AEs and SAEs.

2.3.2 Secondary Endpoint

The secondary endpoint of this trial is:

- Clinical cure determined by the Investigator at 48-72 hours after start of oritavancin dose and Day 7 visit.

2.3.3 Exploratory Endpoint:

An exploratory outcome of this trial is to evaluate the potential for antibody development following a single dose oritavancin administration.

3 STUDY DESIGN

3.1 Number of Subjects

Up to forty subjects will be enrolled at up to 10 centers in the United States (US). Approximately 25 subjects on concomitant warfarin therapy will be enrolled in this study. An additional 15 patients with ABSSSI, who are not on warfarin, will also be enrolled.

3.2 Sample Size Considerations

The sample size of 25 subjects on concomitant warfarin therapy is chosen based on feasibility and clinical judgment to provide adequate safety information on the administration of oritavancin with an ABSSSI who are on chronic warfarin.

An additional group of 15 ABSSSI patients, who are not on chronic warfarin therapy, was added to obtain information regarding potential for antibody production related to oritavancin administration.

3.3 Study Design

This will be a Phase IV, open-label study evaluating the safety and tolerability when a single 1200 mg dose of oritavancin is given concomitantly in subjects on chronic warfarin therapy with ABSSSI. An additional group of patients with ABSSSI, who are not on concomitant warfarin therapy, will also be enrolled.

Up to 40 subjects will be enrolled at up to 10 centers in the United States. Informed consent will be obtained from subjects meeting all inclusion and no exclusion criteria before the initiation of any study-specific procedures.

Eligible subjects will be enrolled and receive a single 1200 mg dose of oritavancin IV.

Adverse events and SAEs will be assessed from the time of informed consent through 14 days post administration of oritavancin.

The schedule of events is shown in [Table 1](#). This schedule is based on Protocol MDCO-ORI-14-03, Amendment 2 (17 March 2016). In Protocol Amendment 1 (dated 16 December 2015), Direct Coombs Test (DAT) was added to the schedule of events; in Protocol Amendment 2, Indirect Coombs Test (IAT) and the drug dependent antibody was added to the schedule of events.

Table 1: Schedule of Events

Study procedures	SCREENING ≤24 hrs from 1st dose	Pre-Dose	Treatment	FOLLOW UP			
				Day 1	Day 2	Day 3 Safety & Efficacy Visit	Day 7 Safety & Efficacy Visit
Informed Consent	x						
Assess Inclusion/Exclusion	x	x					
Medical History	x						
Physical Exam (height and weight at Screening only)	x						
Vital Signs ²	x	x	x		x	x	x
Pregnancy test ³	x					x	
Record ABSSI surgical procedures ⁴	x						
Safety laboratory assessments ⁵	x					x	x
Microbiology testing ⁶	x						
Record prior or concomitant medications	x	x	x	x	x	x	x
Administer IV oritavancin			x				
PT/INR Test ⁷	x			x	x	x	x
Assess clinical cure ⁸					x	x	
Immunoglobulin panel and plasma for oritavancin antibody assay	x				x	x	x
Direct and Indirect Coombs Test ⁹	x				x	x	x
Assessment of adverse events ¹⁰	x	x	x	x	x	x	x
Plasma Storage Samples for Drug Dependent Antibody Ex Vivo Study ¹¹			x				

¹ If subject has abnormal laboratory values that have not returned to a therapeutic baseline by Day 14, additional follow up visits may be required.

² Vitals signs include blood pressure, temperature, respiratory rate and heart rate.

³ Perform a local urine pregnancy test for female patients of childbearing potential (may be omitted for females > 2 years postmenopausal or surgically sterile).

4 GENERAL STATISTICAL CONSIDERATIONS

All analyses described in this plan are considered *a priori* analyses in that they have been defined prior to database lock. All other analyses, if any, designed subsequent to the database lock will be considered *post hoc* analyses and will be applied as exploratory methodology. All *post hoc* analyses will be identified as such in the clinical study report.

Continuous variables will be summarized using mean, standard deviation (SD), median, quartiles (Q1 and Q3), minimum, and maximum. Categorical variables will be summarized using frequency and percentage.

Summary statistics will be presented as follows: number of observations will be presented without any decimal places, minimum/maximum in the same precision as reported values, arithmetic and geometric means/median to 1 more decimal place than the reported values, SD to 1 more decimal place than mean/median, and coefficient of variation (CV) to 1 decimal place.

Data will be summarized by cohort. Summary tables will only be provided for cohorts with more than 4 subjects. For cohorts with no more than 4 subjects, only listings will be provided.

All statistical analyses will be conducted using SAS® version 9.3 or later using procedures appropriate for the particular analysis.

5 ANALYSIS POPULATIONS

Two populations will be used for data analyses and/or presentation.

5.1 Intent-to Treat (ITT) Population

The ITT population will include all subjects screened and enrolled. This will be the primary population for efficacy analysis.

5.2 Safety Population

The safety population will include all subjects who are dosed with IV oritavancin. This will be the primary population for safety analysis.

5.3 Missing Data Handling

Unless otherwise specified, missing data will not be imputed and will be excluded from the associated analysis.

5.4 Key Definitions

Unless otherwise specified, the last evaluation prior to the initiation of study drug will be considered the "Baseline" evaluation for analysis.

6 SUBJECT DISPOSITION AND BASELINE CHARACTERISTICS

6.1 Subject Discontinuation

The number of subjects who enroll in the study and the number and percentage of subjects who complete the study will be presented by cohort. The frequency and percentage of subjects who withdraw or discontinue from the study and the reason for withdrawal or discontinuation will be summarized for the safety population.

A data listing for subject disposition including study completion status and reason for study discontinuation will be provided. In addition, analysis populations and reasons for exclusion from the analysis population will be provided in a data listing.

6.2 Demographics and Baseline Characteristics

Subject demographics and baseline characteristics will be summarized by cohort for the safety populations. Descriptive statistics (i.e., mean, median, SD, minimum, and maximum) will be calculated for continuous demographic and baseline characteristic variables (age, weight, height, and body mass index [BMI]) and frequency counts will be tabulated for categorical demographic variables (sex, race, and ethnicity) for each cohort and overall.

In addition to the summary tables, a data listing will be provided for all demographic data. The height, weight, and BMI will be provided in the vital sign data listing.

6.3 Study Drug and Concomitant Medications

Separate summary of prior (pre-baseline) and concomitant (baseline or later) medications will be provided for the safety population. Medications will be coded with the World Health Organization (WHO) Drug Dictionary Enhanced. Subjects will be counted only once within each period by medication.

Prior medications are those with a start date occurring before the initiation of study drug on Day 1. Concomitant medications are those with a start date occurring on or after the initiation of study drug on Day 1 or that have unknown or ongoing end dates. In the event of a partial date, the medication will be classified as prior.

Prior and concomitant medications will be provided in a data listing by subject.

7 **EFFICACY ANALYSIS**

Efficacy results for all subjects will be provided in data listings.

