## 4.2. INCLUSION CRITERIA

Subjects may be included in the study if they meet all of the following criteria:

- 1. Males or females ≥18 years old
- 2. Diagnosis of ABSSSI (wound infections, Cellulitis/erysipelas, or cutaneous abscess) suspected or confirmed to be caused by a Gram-positive pathogen requiring IV therapy
- 3. Must be currently being treated with chronic warfarin therapy\*:
  - a. Warfarin therapy must have been initiated a minimum of 30 days prior to enrollment
  - b. Current warfarin dosage must be stable for at least 14 days prior to enrollment
  - c. At least one documented INR between 1.5 and 3.0 in the 30 days prior to Screening
  - d. The INR value at Screening must fall within 1.5 and 3.0 and also be within 25% of the prior documented value
- 4. Able to give informed consent and willing to comply with all required study procedures
- \*Patients in the non-warfarin sub-group are not required to be on chronic warfarin therapy

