- 10. Women who are pregnant or nursing, or who are of childbearing potential and unwilling to use at least 2 acceptable methods of birth control: (e.g., prescription oral contraceptives, contraceptive injections, contraceptive patch, intrauterine device, barrier method(s) or male partner sterilization). Women ≥2 years postmenopausal or surgically sterile are exempt from this exclusion
- 11. History of immune-related hypersensitivity reaction to glycopeptides (such as vancomycin, televancin, daptomycin, or dalbavancin) or any of their excipients.

  Note: subjects who have had histamine-like infusion reactions to a glycopeptide are not excluded
- 12. Subjects unwilling to forego blood and/or blood product donation for at least 1 month from initiation of oritavancin dose

- 13. Treatment with investigational medicinal product within 30 days or 5 half-lives, whichever is longer, before enrollment and for the duration of the study
- 14. Investigational device present, or removed within 30 days before enrollment, or presence of device-related infection
- 15. Significant change of any medications over the preceding 7 days that could interfere with the metabolism of warfarin (if patient is on chronic warfarin therapy)
- 16. Subjects who the investigator considers unlikely to adhere to the protocol, comply with oritavancin administration, or complete the clinical study (e.g., unlikely to survive 90 days from initiation of oritavancin dosing)

Subjects excluded for any of the previous criteria may only be rescreened for participation after favorable discussion with sponsor and principal investigator

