# **6.2.** SCREENING PERIOD (≤24 HRS PRIOR TO DAY 1)

The following procedures will be performed  $\leq$  24 hours prior to Day 1 to establish each candidate's general health and qualifications for enrollment into the study:

- Obtain written informed consent
- Verify inclusion/exclusion criteria
- Record medical history and demographics
- Obtain height and weight to determine body mass index (BMI)
- Perform a physical examination
- Obtain vital sign measurements (blood pressure, heart rate, respiratory rate and temperature)
- Collect blood specimens for hematology, serum chemistry, immunoglobulin panel, oritavancin antibody assay, PT/INR coagulation test, direct and indirect Coombs test
- A urine pregnancy test will be performed for female subjects of childbearing potential. This test may be omitted for females >2 years postmenopausal or surgically sterile.
- Microbiology samples, if obtained, per standard of care
- Record medication history over the past 14 days, including over-the-counter (OTC), prescription drugs, vitamins and nutraceuticals (e.g., herbal supplements)

- Assessment of AEs and SAEs starting from the time the informed consent form is signed
- Record planned ABSSI surgical procedures

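### SAP 6.3 tabulates a drug started before dosing and stopped on a known later date as prior only, against Protocol 10.3.2; its partial-date rule is ambiguous; and no output summarises the recorded warfarin dose changes

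*SAP*

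**What the plan says.** **Classification of medications.** Protocol 10.3.2 classifies by time of receipt: "Prior medications are those received before the initiation of dosing on Day 1 while concomitant medications are those received after". A drug taken on both sides of the dose meets both descriptions.

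SAP 6.3 opens in the same spirit: "Separate summary of prior (pre-baseline) and concomitant (baseline or later) medications will be provided for the safety population". Its operative definitions then change the basis. Prior is decided by a start date before dosing. The concomitant class takes in any drug "with a start date occurring on or after the initiation of study drug on Day 1 or that have unknown or ongoing end dates". Two further rules follow: "In the event of a partial date, the medication will be classified as prior", and "Subjects will be counted only once within each period by medication". A by-subject listing of all prior and concomitant medications is also planned.

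**Warfarin dosing.** Protocol 1.3 gives as the study's intention to establish how large and how long-lasting any alterations to warfarin dosing are. The synopsis (Additional Safety Evaluation) and Protocol 5.2.3 require dose changes prompted by PT/INR or safety data to be collected. The SAP does not mention warfarin dose as something to be tabulated.

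**The concern.** The concomitant table is where a reader looks for drugs that were on board after oritavancin and could have affected warfarin or bleeding risk. The protocol leaves room for such drugs to have begun before dosing. Section 5.2.1 discourages only new interacting drugs, and the relevant exclusion in section 4.3 covers only "Significant change of any medications over the preceding 7 days that could interfere with the metabolism of warfarin". An interacting drug that had been stable for longer, and was then stopped on a known date after dosing, is therefore permitted. It would nevertheless be absent from the concomitant table.

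The same applies to warfarin itself. For this cohort, "Warfarin therapy must have been initiated a minimum of 30 days prior to enrollment", so the original warfarin record always starts before dosing and can reach the concomitant table only through its end date. A subject whose warfarin was stopped on a known post-dose date and not restarted would be shown as having had warfarin beforehand only. That is a subject whose anticoagulation changed in the period the study set out to observe.

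The missing dose-change summary matters for a related reason. SAP 8.2 summarises PT/INR and its change from baseline. Those values are hard to interpret without knowing whose warfarin dose was altered, when and in which direction.

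**Working it through.** There is no figure to reproduce. The check applies the SAP 6.3 rules literally to each pattern of dates and compares the result with Protocol 10.3.2.

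| Start | End | SAP 6.3 | Protocol 10.3.2 | Result |
|---|---|---|---|---|
| Before dosing | Known, before dosing | Prior | Prior | Agree |
| Before dosing | Known, after dosing (e.g. Day 5) | Prior only | Prior and concomitant | Mismatch |
| Before dosing | Ongoing | Prior and concomitant | Prior and concomitant | Agree |
| Before dosing | Unknown | Prior and concomitant | Depends on actual receipt | SAP default is reasonable |
| On or after dosing | Known | Concomitant | Concomitant | Agree |
| Partial | Ongoing | Concomitant by the ongoing branch; prior by the partial-date sentence | Concomitant | Conflict if the partial-date sentence is exclusive |
| Partial, consistent with a pre-dose start | Known, after dosing | Prior; no concomitant branch applies | Concomitant | Mismatch |
| On or after dosing | Partial | Concomitant by start date; prior if the partial-date sentence covers end dates | Concomitant | Conflict if end dates are covered |

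These rows are kinds of record. They say nothing about how often each kind occurs.

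**Known post-dose stop.** The definition of concomitant has two branches: a start on or after dosing, or an end date that is unknown or ongoing. A pre-dose start with a known later end satisfies neither. The cause is a missing branch, and no assumption about data quality is needed.

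**Partial dates.** The sentence leaves two things open: which date it means, and whether being classified as prior excludes also being concomitant. If it is exclusive, it overrides the ongoing branch for a drug with an incomplete start date. If it covers end dates, a drug first taken after dosing can be labelled prior, which is wrong whether or not the label is exclusive.

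**Effect on the warfarin count.** A fully dated, ongoing warfarin record is both prior and concomitant, which is correct. Subjects are counted once per medication within each period. If a dose change is entered as a new record, that record starts after dosing and keeps the subject in the concomitant count. A subject is lost only if none of their warfarin records qualifies.

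**Search for a warfarin-dose output.** The SAP plans disposition (6.1), demographics (6.2), medication summaries and a listing (6.3), efficacy listings (7), adverse events (8.1), laboratory values (8.2), vital signs (8.3) and a listing of study drug administration (8.4). Sections 9 and 10 plan nothing. No output summarises warfarin dose changes. The medication listing may show them if they were entered as medication records, but the SAP does not say so.

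**The case against.** The strongest reply is that little depends on this. With about 25 warfarin subjects, a by-subject listing can be read from end to end. The cohort is defined by warfarin use, so nobody needs the concomitant table to learn who took it. PT/INR is summarised in any case. Warfarin dose change is not a named primary, secondary or exploratory outcome, Protocol section 10 promises no table of it, and whether size and duration can be tabulated depends on an eCRF that the documents do not show. All of this stands, and it is why the classification error is minor. It does not make the rule correct: a summary table labelled concomitant would still omit drugs that the protocol defines as concomitant.

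A second reply is that SAP 6.3 does not make the classes exclusive, since an ongoing drug with a full pre-dose start meets both definitions. The partial-date sentence could then merely settle an incomplete start date and leave the ongoing branch intact. That reading is available, so the clash over a partial start with an ongoing end is an ambiguity and not a certain contradiction. It does not rescue the known post-dose stop, where no concomitant branch exists on any reading.

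A reader might also infer that warfarin start dates are likely to be partial, because sites are told to "Record medication history over the past 14 days" while warfarin began well before that. The documents do not support the inference. The window limits which drugs are asked about, not how completely their dates are recorded, and sites must establish the warfarin start in order to confirm eligibility.

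**Conclusion.** The point holds in a limited form.

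- **Classification:** wrong as written for drugs started before dosing and stopped on a known date afterwards. It contradicts Protocol 10.3.2 and the lead-in to SAP 6.3 itself. A drug both started and stopped after dosing, with complete dates, is classified correctly.
- **Partial dates:** ambiguous, with misclassification on some readings.
- **Size:** minor. The records remain in the prior summary and the listing. The primary endpoint in SAP 2.3.1 rests on vital signs, laboratory abnormalities and adverse events, none of which uses this classification. The documents give no frequency for the affected records, and none is assumed here.
- **Warfarin dose changes:** a real gap against the intention stated in Protocol 1.3, using data the protocol already requires. A reader might infer that the SAP has dropped an analysis the protocol planned. It has not, because Protocol section 10 plans none.

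The conclusion rests on reading the SAP 6.3 definitions literally, as a programmer would. Nor should it be read as meaning that warfarin would generally drop out of the concomitant table: fully dated ongoing warfarin stays in.

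**What to change.** **1. Rewrite the definitions in SAP 6.3.** Define a medication as concomitant if its start date is on or after the start of oritavancin, or its end date is on or after it, or its end is ongoing or unknown. State that a drug may be both prior and concomitant. Replace the partial-date sentence with separate rules for the two dates:

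- A partial start date counts as prior unless its known parts show a start on or after dosing.
- A drug counts as concomitant unless its end date, or the known parts of a partial end date, shows that it stopped before dosing.

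Under these rules a partial start with a complete pre-dose stop remains prior only, a partial start with an ongoing end is both, and a post-dose start with a partial end is concomitant only.

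**2. Add one descriptive table for the warfarin cohort.** Give n (%) with any recorded warfarin dose change or interruption, with direction, size, timing and duration as far as the eCRF captured them. Footnote the limit of follow-up: about Day 14 under Protocol section 6, apart from any extended PT/INR follow-up under Protocol 7.2.4.

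**Cost.** A few sentences and one short table, with no new visits, tests or data. The detail of the table depends on what the eCRF recorded. If the SAP is already final, its introduction requires the change to be documented.
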